## Summaries through Week 16 (placebo controlled):

Safety data through Week 16 will be summarized by treatment groups

- 1. Placebo
- 2. Bermekimab 400 mg q2w
- 3. Bermekimab 400 mg qw
- 4. Combined Bermekimab

This allows between-group comparisons of safety between the bermekimab regimens and the placebo group based on similar follow-up period in each group.

#### Summaries through Week 36

Safety data through Week 36 will be summarized by treatment groups including

- 1. Placebo  $\rightarrow$  bermekimab 400 mg qw
- 2. Bermekimab 400 mg q2w
- 3. Bermekimab 400 mg qw
- 4. Combined Bermekimab

This allows safety comparisons between each bermekimab regimen through Week 36 based on the similar follow-up time in each group.

The list of actual treatment groups for safety analyses and inclusions of participants and safety events/measurements in each group are defined as follows:

- 1. **Placebo:** all participants who were randomized to placebo at Week 0 and received treatment with placebo only or received treatment with placebo prior to receiving treatment with bermekimab. For participants who started treatment with placebo but later received bermekimab, the safety events/measurements on and after the first dose of bermekimab will be excluded from this group. Only the safety events/measurements that occurred while the participants had been receiving placebo only will be included in this group.
- Placebo → bermekimab 400 mg qw: All participants who were randomized to placebo at Week 0 started treatment with placebo only and later crossed over to receive treatment with bermekimab 400 mg SC (qw). Only the safety events/measurements from these participants that occurred on and after their first administration of bermekimab will be included in this group.
- 3. **Bermekimab 400 mg q2w:** all participants who were randomized to bermekimab 400 mg SC (q2w) at Week 0 and received bermekimab. All the safety events/measurements from these participants that occurred from Week 0 will be included in this group.
- 4. **Bermekimab 400 mg qw:** all participants who were randomized to bermekimab 400 mg SC (qw) at Week 0 and received bermekimab. All the safety events/measurements from these participants that occurred from Week 0 will be included in this group.

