## 4.4. Extent of Exposure

The exposure data through Week 16 and through Week 36 will be summarized. The number and percentage of participants who receive study agent will be summarized by treatment group for the safety analysis set. Descriptive statistics will be presented for the following parameters:

- Number of administrations
- Cumulative total dose

In addition, the average exposure (number of administrations) and average duration of follow-up (weeks) will also be summarized by treatment group in the safety tables through different study time periods.

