## 6. SAFETY

Safety will be assessed by summarizing the incidence and type of AEs and examining changes in laboratory parameters (hematology, chemistry, and inflammatory markers), and vital signs.

In all the safety analysis, randomized participants who received at least 1 (partial or complete) dose of study agent administration will be included. For safety analyses, participants will be analyzed according to the randomized treatment groups they were assigned to, regardless of the treatments they actually received. No formal statistical comparison is planned.

Depending on the safety data categories, the cumulative safety data will be analyzed through different study periods through Week 16 and Week 36. Unless otherwise specified, tabular summaries of safety events for key study periods are in general presented as following:

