## 6.1. Adverse Events

The verbatim terms used in the eCRF by investigators to identify adverse events will be coded using the Medical Dictionary for Regulatory Activities (MedDRA). Any AE starting at or after the initial administration of study agent through the end of the trial is considered to be treatment emergent. If the event occurs on the day of the initial administration of study agent, and either event time or time of administration are missing, then the event will be assumed to be treatment emergent. If the event date is recorded as partial or completely missing, then the event will be considered to be treatment emergent unless it is known to be prior to the first administration of study agent based on partial onset date or resolution date. All reported treatment-emergent adverse events will be included in the analysis.

The following analyses will also be used to assess the safety of participants in the study:

- The incidence and type of AEs.
- The incidence and type of SAEs.

- AEs of severe intensity
- AEs that led to permanent discontinuation of study agent administration
- The incidence and type of reasonably related AEs.

In addition, a participant who had injection site reaction(s) in 30 minutes (+/-10) post injection at Weeks 0, 1, and 2 were recorded in eCRF. The incidence of injection-site reaction during this time frame will be summarized.

These summary tables will provide the count and percentage of participants with 1 or more of the specified AEs by treatment group. In addition to the summary tables, listings will be provided for participants who:

- Had SAEs.
- Had AEs leading to discontinuation of study.
- Had AEs of severe or life threating, or fatal based on CTCAE (grade  $\geq$ 3) intensity.
- Had anaphylactic or serum sickness-like reactions.

Since safety should be assessed relative to exposure and follow-up, most AE summary tables will include average weeks of follow-up and average number of study agent administrations, infusions and injections for each treatment group. A listing of participants who died will be provided.

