#### 6.2. Clinical Laboratory Tests

All clinical laboratory reports will be displayed for the participants included in the safety analysis set. The clinical laboratory parameters to be evaluated by the central laboratory include but are not limited to:

- Hematology: Complete Blood Count (CBC) with differential, platelets, and hemoglobin.
- Chemistry: albumin, alkaline phosphatase, alanine aminotransferase, aspartate aminotransferase, total bilirubin, blood urea nitrogen/urea, calcium, chloride, creatinine, GGT, glucose, potassium, total protein, sodium, bicarbonate.

Box plots of laboratory measurements and change from baseline will be provided for the selected laboratory measurement.

Applicable laboratory results will be graded according to National Cancer Institute's Common Terminology Criteria for Adverse Events (NCI-CTCAE version 5.0). The worst NCI-CTCAE will be summarized by treatment group.

A listing of participants with 1 or more NCI-CTCAE toxicity grade  $\geq 2$  in hematology and clinical chemistry laboratory measurements will be provided

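### SAP 6 claims similar follow-up in every through-Week-36 safety group, but Placebo→qw is observed for about 20 weeks against 36 for q2w and qw

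*SAP*

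**What the plan says.** SAP 6 plans two sets of safety summaries. The through-Week-16 set shows placebo, q2w, qw and combined bermekimab. The through-Week-36 set shows Placebo→qw, q2w, qw and combined bermekimab, and closes with: "This allows safety comparisons between each bermekimab regimen through Week 36 based on the similar follow-up time in each group".

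The group definitions follow directly. For Placebo→qw: "Only the safety events/measurements from these participants that occurred on and after their first administration of bermekimab will be included in this group". For q2w and for qw: "All the safety events/measurements from these participants that occurred from Week 0 will be included in this group". SAP 1.2 puts the switch of Arm 3 to bermekimab at Week 16, and Protocol 5.1 puts the last visit at Week 36.

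The statistics are crude. SAP 6.1 says of adverse events: "These summary tables will provide the count and percentage of participants with 1 or more of the specified AEs by treatment group". SAP 6.2 says of laboratory grades: "The worst NCI-CTCAE will be summarized by treatment group".

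Three statements limit the effect. SAP 6 says: "No formal statistical comparison is planned". SAP 6.1 says that "most AE summary tables will include average weeks of follow-up and average number of study agent administrations, infusions and injections for each treatment group". SAP 4.4 adds that "average duration of follow-up (weeks) will also be summarized by treatment group in the safety tables through different study time periods".

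**The concern.** The sentence gives a reader of the Week 36 tables a reason to compare columns directly, but one of the listed groups does not have the stated property. The percentage with at least one event can only rise with observation time, and the worst grade can only rise with the number of draws. A group watched for a little over half as long will tend to show lower figures even when its risk is the same.

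No planned table corrects for this. The through-Week-16 tables hold only the placebo time of these participants. The through-Week-36 tables set their roughly 20 weeks beside 36. Nowhere does the crossover group stand beside q2w and qw over the same time since first bermekimab. At stake is a fair descriptive reading of safety in the participants who start bermekimab at Week 16.

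**Working it through.** **Inputs.** Week 16 is day 112 ±3 and Week 36 is day 252 ±3 (Protocol 5.1). Counting starts as defined in SAP 6. Chemistry and hematology are drawn after baseline at Weeks 8, 12, 16, 24, 32 and 36, and the Week 16 sample is taken before the injection (Protocol 5.1 and 5.2). Dosing is weekly from Week 0 to Week 31. About 150 participants are randomized 1:1:1, so about 50 per arm.

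**Step 1: the plan's own statement.** It is given in words, not as a number. Planned follow-up = (last day − first counted day)/7.

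| Group | Follow-up | Scheduled post-dose draws | Dosing visits |
|---|---|---|---|
| q2w | 252/7 = 36 weeks | 6 | 32 (active and placebo) |
| qw | 252/7 = 36 weeks | 6 | 32 |
| Placebo→qw | (252 − 112)/7 = 20 weeks | 3 (Weeks 24, 32, 36) | 16 |

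The visit windows move 20 weeks to between 19.1 and 20.9. The ratio is 20/36 = 0.56. The statement reproduces for q2w versus qw and fails for Placebo→qw.

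**Step 2: adverse-event percentages.** The documents give no event rates for these groups, so the incidences are assumed. Risk is taken as equal by time since first dose. With a constant hazard, P(20) = 1 − (1 − P(36))^(20/36).

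| Assumed incidence at 36 weeks | Seen at 20 weeks |
|---|---|
| 10% | 5.7% |
| 30% | 18.0% |
| 50% | 32.0% |
| 70% | 48.8% |

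If the hazard in the first 4 weeks is k times the later hazard, the exponent becomes (4k + 16)/(4k + 32). For 50% at 36 weeks, k = 3 gives 35.7% and k = 5 gives 38.1%. The gap shrinks from 18 points to 14 or 12.

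**Step 3: worst laboratory grade.** Assume a chance p per draw of reaching a given grade. With independent draws the chance of seeing it at least once is 1 − (1 − p)^n. For correlated draws a beta-binomial model is used.

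| p per draw | Within-patient correlation | 3 draws | 6 draws |
|---|---|---|---|
| 5% | 0 | 14.3% | 26.5% |
| 10% | 0 | 27.1% | 46.9% |
| 10% | 0.3 | 20.8% | 29.4% |
| 10% | 0.5 | 17.4% | 22.3% |

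**Step 4: a window that can be matched.** Take 16 weeks from first bermekimab.

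- Dosing visits: Weeks 0–15 = 16 for q2w and qw; Weeks 16–31 = 16 for crossover.
- Draws at 8 and 16 weeks after first bermekimab: Weeks 8 and 16 against Weeks 24 and 32, so 2 against 2. The Week 12 draw has no crossover counterpart, because none is scheduled at Week 28.
- Active visits in q2w: 2 loading visits plus half of the 14 visits in Weeks 2–15, so 2 + 7 = 9 of 16.

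**The case against.** The strongest defence is that the sentence speaks of bermekimab regimens. The two randomized regimens are q2w and qw, and their follow-up is equal. The definitions beneath it state openly that crossover events count only from first bermekimab. SAP 6.1 itself says that safety should be judged against exposure and follow-up, most adverse-event tables will show both, and SAP 4.4 extends the display to safety tables in general. No formal comparison is planned.

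Much of this stands. The imbalance will be visible, and nothing is hidden. But the sentence ends by referring to each group, after a list headed by Placebo→qw, and display is not adjustment. If the narrow reading was meant, saying so costs a few words.

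The sizes in the working rest on assumed rates, and that also stands. The one reaction rate the Protocol gives (section 9.7: 27 of 911, 3.0%, injection-site or infusion reactions) would produce little distortion. Treated as a 36-week incidence, which is an assumption, it becomes 1 − 0.97^(20/36) = 1.7% at 20 weeks, a gap of less than one patient in 50. Unscheduled and early-termination visits can also add draws to the scheduled counts.

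Follow-up is also not the same as dosing. Through Week 31, q2w has 2 + 15 = 17 active visits against 16 in crossover. That is a fair caution for any exposure comparison, but the SAP's sentence is about follow-up time.

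A reader might infer that all 20 crossover weeks should be matched. The documents do not support that as an on-treatment comparison. The last dose is at Week 31, the Week 36 draw comes about 5 weeks later, and no visit is scheduled between Weeks 32 and 36.

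**Conclusion.** The statement of similar follow-up is true for q2w versus qw (36 weeks each) and untrue for Placebo→qw (about 20 weeks and 3 scheduled draws against 6). At equal true risk by time since first dose, crude adverse-event percentages and worst grades would tend to look lower in the crossover group. For common events the gap could be 12 to 18 points under the assumed 50% incidence; for rare events it is a point or two. The 20 and 36 weeks are planned maxima, and dropout would shorten them.

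The point is worth correcting, but its reach is small. Three stronger readings are not supported:

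- A reader might infer that a trial conclusion is at risk. Safety is descriptive, average follow-up is shown, and the Week 12 primary test does not use these tables.
- A reader might infer that the crossover group is bound to look safer. That follows only if true risk is equal. This group starts without a loading dose and contains only participants still treated at Week 16, so its risk may differ either way.
- A reader might infer that the through-Week-36 combined column carries the same mismatch. SAP 6 lists that column but does not define it, so the text does not settle whether crossover time is included.

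**What to change.** (a) In SAP 6, limit the similar-follow-up sentence to q2w versus qw, and state that Placebo→qw covers about 20 weeks from first bermekimab.

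(b) Add a display that sets Placebo→qw beside q2w and qw over a matched on-treatment window of 16 weeks from first bermekimab:

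- Adverse events: Weeks 16–32 for crossover, Weeks 0–16 for q2w and qw, with 16 weekly dosing visits in each.
- Worst laboratory grade: the draws at 8 and 16 weeks after first bermekimab, that is Weeks 24 and 32 for crossover and Weeks 8 and 16 for q2w and qw.

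Footnote what stays unequal: q2w visits alternate active drug and placebo (9 of 16 visits active), crossover has no loading dose, and crossover includes only participants still treated at Week 16.

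The cost is one corrected sentence and a few extra tables from data already collected, with no change for participants or sites. The small downside is that the window leaves out later follow-up, which stays in the through-Week-36 tables.

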## 6.1. Adverse Events

The verbatim terms used in the eCRF by investigators to identify adverse events will be coded using the Medical Dictionary for Regulatory Activities (MedDRA). Any AE starting at or after the initial administration of study agent through the end of the trial is considered to be treatment emergent. If the event occurs on the day of the initial administration of study agent, and either event time or time of administration are missing, then the event will be assumed to be treatment emergent. If the event date is recorded as partial or completely missing, then the event will be considered to be treatment emergent unless it is known to be prior to the first administration of study agent based on partial onset date or resolution date. All reported treatment-emergent adverse events will be included in the analysis.

The following analyses will also be used to assess the safety of participants in the study:

- The incidence and type of AEs.
- The incidence and type of SAEs.

- AEs of severe intensity
- AEs that led to permanent discontinuation of study agent administration
- The incidence and type of reasonably related AEs.

In addition, a participant who had injection site reaction(s) in 30 minutes (+/-10) post injection at Weeks 0, 1, and 2 were recorded in eCRF. The incidence of injection-site reaction during this time frame will be summarized.

These summary tables will provide the count and percentage of participants with 1 or more of the specified AEs by treatment group. In addition to the summary tables, listings will be provided for participants who:

- Had SAEs.
- Had AEs leading to discontinuation of study.
- Had AEs of severe or life threating, or fatal based on CTCAE (grade  $\geq$ 3) intensity.
- Had anaphylactic or serum sickness-like reactions.

Since safety should be assessed relative to exposure and follow-up, most AE summary tables will include average weeks of follow-up and average number of study agent administrations, infusions and injections for each treatment group. A listing of participants who died will be provided.

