In order to maintain blinding, all patients will receive two injections at week 0 and 1, followed by weekly injections from weeks 2 to 31. Additionally, at least one qualified individual will be designated at each study site to perform all preparation and injection of the investigational product. The designated injector should have no other contact with the participant during the study, should not discuss the participant's treatment with the participant, participant's caregiver, or other site personnel at any time, and will not be permitted to review the participant's medical records, questionnaires, or the electronic CRF prior to each injection. The designated injector should be documented in the source documents at each visit.

Study treatment will be administered weekly in the clinic for 31 weeks with weekly office visits for 32 weeks. Patients will remain at the study site for a minimum of 30 minutes (+/- 10 minutes) after injections at weeks 0, 1, 2, 16, 17 and 18 injections for safety monitoring.

During the 32-week treatment period, patients will attend weekly clinical study visits. Clinical assessments, collection of samples for bermekimab concentrations, and safety testing will be performed at specified clinic visits. The primary endpoint data will be collected at week 12. After completion of the 36-week study period, data will be locked and analyzed for safety and efficacy endpoints for all arms. In addition to the analyses that will be performed following the formal database lock at the end of the study at Week 36, an additional database lock may be performed at Week 16, and interim analyses utilizing unblinded efficacy data available as the study progresses, may also be conducted to help plan potential future development activities. An internal interim analysis committee (IAC) will be established to review the

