5. TREATMENT PLAN

5.1 STUDY PROCEDURES

PLACEBO-CONTROLLED PERIOD

Screening (maximum 30 days): The screening period begins once the informed consent is signed.

- Informed Consent
- Inclusion/ Exclusion
- Medical History/ Demographics
- Height, Weight, Body Mass Index (BMI) [BMI= weight (kg)/height (m2)]
- Concomitant Medications/treatments
- Provide subject copies of the patient take home diary, which will consist of NRS pain (worst moment, average & current) and itch (worst moment & average) assessments to be completed by patients daily.
- Lesion Counts (HiSCR), mHSS, HS-PGA, PGA-ISD, IHS4, Hurley Staging
- DLQI, HADS, PGI-c, PGI-s, EQ-5D-3L, HSSD, HiSQOL
- Physical Exam
- Electrocardiogram
- Vital Signs (blood pressure, pulse, oxygen saturation, respiratory rate and body temperature)
- Urinalysis: pH, protein, glucose and blood cells (RBCs and WBCs)
- Blood Draw:
 - o Chemistry panel: Albumin, Alkaline Phosphatase, ALT, AST, GGT,

Bicarbonate (CO2), Calcium, Chloride, Creatinine, Glucose, Potassium, Sodium, Total Bilirubin, Total Protein, Urea Nitrogen (BUN)

- Hematology Panel: Complete Blood Count (CBC) with differential and platelets
- Infectious disease panel: HIV antibody, Hepatitis C antibody, Hepatitis B panel (HBsAg, anti-HBc, anti-HBs), and interferon gamma release assay (IGRA) for TB
- Serum pregnancy test for WOCBP
- Inflammation Markers: CRP (C-Reactive Protein), ESR (Erythrocyte Sedimentation Rate)
- Randomization to study arm (once confirmed patient has passed screening requirements).

***Patients will be monitored at the study site at visits 1, 2, 3, 17, 18 & 19 (weeks 0, 1, 2, 16, 17 & 18) for a minimum of 30-minutes after study drug administration. Vital signs and AE assessments will be done at 30 minutes (+/- 10 minutes) post-injection. ***

Visit 1 (Week 0) (day 0, must occur within 30 days of signing informed consent):

- At least 45 minutes before injection: Remove syringe from refrigeration and lay flat; allow to warm to room temperature. Do not heat
- Pre-injection
 - Verify patient still meets inclusion/exclusion criteria
 - Height, Weight, Body Mass Index (BMI) [BMI= weight (kg)/height (m2)]
 - Patient Diary
 - Baseline Lesion Counts (for future HiSCR assessments), mHSS, HS-PGA, PGA-ISD, IHS4 and Hurley Staging
 - o DLQI, HADS, PGI-c, PGI-s, EQ-5D-3L, HSSD, HiSQOL
 - Physical Exam, Vital signs, Urine pregnancy
 - o Urinalysis
 - Blood draw for chemistry, hematology, inflammation markers, PK/ADA, IL-6,

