	⁶ Loading Doses: Treatment arm 1: 800 mg loading dose of bermekimab (2 x 400 mg SC injections) at weeks 0 and 1; Treatment arm 2: 800 mg loading dose of bermekimab (2 x 400 mg SC injections) at weeks 0 and 1; Arm 3: 800 mg loading dose of placebo (2 x 400 mg SC injections) at weeks 0 and 1; Arm 3: 800 mg loading dose of placebo (2 x 400 mg SC injections) at weeks 0 and 1; Arm 3: 800 mg loading dose of placebo (2 x 400 mg SC injections) at weeks 0 and 1; Arm 3: 800 mg loading dose of placebo (2 x 400 mg SC injections) at weeks 0 and 1; Arm 3: 800 mg loading dose of placebo (2 x 400 mg SC injections) at weeks 0 and 1; Arm 3: 800 mg loading dose of placebo (2 x 400 mg SC injections) at weeks 0 and 1; Arm 3: 800 mg loading dose of placebo (2 x 400 mg SC injections) at weeks 0 and 1; Arm 3: 800 mg loading dose of placebo (2 x 400 mg SC injections) at weeks 0 and 1; Arm 3: 800 mg loading dose of placebo (2 x 400 mg SC injections) at weeks 0 and 1; Arm 3: 800 mg loading dose of placebo (2 x 400 mg SC injections) at weeks 0 and 1; Arm 3: 800 mg loading dose of placebo (2 x 400 mg SC injections) at weeks 0 and 1; Arm 3: 800 mg loading dose of placebo (2 x 400 mg SC injections) at weeks 0 and 1; Arm 3: 800 mg loading dose of placebo (2 x 400 mg SC injections) at weeks 0 and 1; Arm 3: 800 mg loading dose of placebo (2 x 400 mg SC injections) at weeks 0 and 1; Arm 3: 800 mg loading dose of placebo (2 x 400 mg SC injections) at weeks 0 and 1; Arm 3: 800 mg loading dose of placebo (2 x 400 mg SC injections) at weeks 0 and 1; Arm 3: 800 mg loading dose of placebo (2 x 400 mg SC injections) at weeks 0 and 1; Arm 3: 800 mg loading dose of placebo (2 x 400 mg SC injections) at weeks 0 and 1; Arm 3: 800 mg loading dose of placebo (2 x 400 mg SC injections) at weeks 0 and 1; Arm 3: 800 mg loading dose of placebo (2 x 400 mg SC injections) at weeks 0 and 1; Arm 3: 800 mg loading dose of placebo (2 x 400 mg SC injections) at weeks 0 and 1; Arm 3: 800 mg loading dose of placebo (2 x 400 mg SC injections) at weeks 0 and 1; Arm 3: 800																	
or placebo (2 x 400 mg SC mjections) at weeks 0 and 1.																		

⁷ Patients in Arm 3 will begin to receive active bermekimab therapy from visit 17 (week 16). Patients in all arms will remain blinded through end of study.

Blinded Active Dosing Period

Study Procedure			Blinded Active Dosing Period													
Visit (V)	V18	V19	V20	V21	V22	V23	V24	V25	V26	V27	V28	V29	V30	V31	V32	V33

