7. ASSESSMENT OF SAFETY

Safety will be assessed by monitoring adverse events, vital signs, and clinical laboratory measurements. Data from ECG will be included in safety analysis only when all of these measures are available for each subject (baseline and last visit). Adverse events will be monitored from visit 1 (week 0) (post-injection) through visit 33 (week 32) as well as during the 4-week follow up period (visit 34 at week 36). Any serious adverse events whether related or not to study drug will be followed up until resolution.

Study drug, bermekimab, will be administered under close observation in a facility equipped to handle anaphylaxis or injection site reactions. Subjects must be closely monitored at the study site at visits 1, 2, 3, 17, 18 & 19 (for the first three injections) until at least 30 minutes following the administration of the antibody. Vital signs and AE assessments will be done at 30 minutes (+/- 10 minutes) post-injection.

Any grade 3 or greater adverse event or injection site reaction must be reported to the sponsor within 24 hours of learning of the event.

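### SAP 6.1 summarises 30-minute injection-site reactions at Weeks 0, 1 and 2 only, leaving out Weeks 16, 17 and 18, when the placebo arm receives its first three bermekimab doses

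*SAP*

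**What the plan says.** SAP 6.1 (Adverse Events) adds one dedicated table to the general adverse-event summaries. Its scope is given as "a participant who had injection site reaction(s) in 30 minutes (+/-10) post injection at Weeks 0, 1, and 2 were recorded in eCRF", and the next sentence reads "The incidence of injection-site reaction during this time frame will be summarized". No other SAP section adds a 30-minute summary for later visits.

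The protocol schedules six observation visits, not three. Section 3 keeps patients on site for about half an hour "after injections at weeks 0, 1, 2, 16, 17 and 18 injections for safety monitoring", and section 5.1 gives the same list as "visits 1, 2, 3, 17, 18 & 19 (weeks 0, 1, 2, 16, 17 & 18"). Section 7 repeats the list and attaches a reason to it: "Subjects must be closely monitored at the study site at visits 1, 2, 3, 17, 18 & 19 (for the first three injections"). It then states what is done: "Vital signs and AE assessments will be done at 30 minutes (+/- 10 minutes) post-injection". Section 9.7 presents observation over the first three doses as the way the class risk of infusion and injection reactions is mitigated, and lists injection site reactions as one of two expected events.

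The second set of visits matches the crossover. Footnote 7 to the calendar in section 5.2.1 says "Patients in Arm 3 will begin to receive active bermekimab therapy from visit 17 (week 16"). Dosing in that arm is weekly from then on.

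**The concern.** The three visits missing from the SAP table are the three at which Arm 3 first meets the drug. In the table as specified, every Arm 3 participant is counted while on placebo and none while on bermekimab. The SAP's own safety section defines a Placebo→bermekimab 400 mg qw group that counts events on and after the first bermekimab dose, but a table restricted to Weeks 0 to 2 can never populate it.

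At stake is the description of acute tolerability on first exposure. About a third of the participants expected to start bermekimab would be missing from the one table built for that purpose. The missing third also differs in kind. Arms 1 and 2 begin with two 400 mg injections at one visit, while Arm 3 begins bermekimab with a single 400 mg injection. The SAP gives no reason for the narrower scope.

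**Working it through.** There is no planned figure to reproduce. The check is a comparison of schedules, followed by simple counts.

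**Schedules side by side**

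| Week | Protocol 30-minute observation (sections 3, 5.1, 7) | SAP 6.1 table | Arm 3 receives |
|---|---|---|---|
| 0, 1, 2 | yes | yes | placebo |
| 16, 17, 18 | yes | no | bermekimab doses 1, 2, 3 |

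Removing {0, 1, 2} from {0, 1, 2, 16, 17, 18} leaves {16, 17, 18}. Three of six observation visits are omitted, and they are exactly Arm 3's first three active doses.

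**Participants affected**

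- Inputs: about 150 randomized and treated at 1:1:1 (SAP 1.4 and 1.5.1), so 150/3 = 50 per arm.
- First exposures inside the table: Arms 1 and 2, 50 + 50 = 100 participants.
- First exposures outside it with no loss before Week 16: 50 participants, 50/150 = 33% of all who start bermekimab, and 50 × 3 = 150 participant-visits.
- With an assumed 20% loss in Arm 3 before Week 16 (the documents give no dropout rate): 40 participants, 40/140 = 29%, and 40 × 3 = 120 participant-visits.

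**What the added participants would buy**

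If no reaction is seen in n participants, the exact one-sided 95% upper limit for the incidence is 1 − 0.05^(1/n).

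| First exposures counted | n | Upper limit |
|---|---|---|
| Arms 1 and 2 only (as written) | 100 | 2.95% |
| All arms, 20% of Arm 3 lost | 140 | 2.12% |
| All arms, no loss | 150 | 1.98% |
| Arm 3 alone, no loss | 50 | 5.8% |
| Arm 3 alone, 20% lost | 40 | 7.2% |

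The pooled rows combine two-injection with one-injection first exposures, so they describe a mixed population. The last two rows show what a separate Arm 3 column could say by itself.

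**The case against.** The strongest reply is that little is lost. The Week 36 safety tables carry a Placebo→bermekimab column, all reported treatment-emergent events enter the analysis, anaphylactic and serum sickness-like reactions are listed, and vital signs are summarized over time. A reader might infer from SAP 6.1 that reactions at Weeks 16 to 18 drop out of safety reporting. The documents do not support that: a reaction reported as an AE at those visits is tabulated. This part of the reply stands and limits the point to one table. It does not remove the point, because the general tables count reactions at any time after any dose and so do not give the 30-minute incidence on first exposure.

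A second reply is that Weeks 0 to 2 are the observation visits with a concurrent placebo group, so a controlled-period table is a reasonable choice in a section where no formal comparison is planned. That would be defensible if the SAP said so. It does not.

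Third, the SAP sentence describes what the eCRF recorded, and the eCRF is not available here. The protocol requires a general AE assessment at 30 minutes, not a dedicated injection-site field. If that field exists only for Weeks 0 to 2, the gap lies in data capture as well as in analysis. This uncertainty stands and bears on the cost of the change.

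Three stronger readings are tempting and should be resisted:

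- Arm 3 might seem to offer the only within-patient comparison of placebo and active injections. It does not, because Arm 2 alternates bermekimab with matching placebo.
- The 3.0% rate in protocol 9.7 (27 of 911) might seem a basis for precision figures. It pools infusion with injection reactions and is not tied to a 30-minute window.
- A table of the first three bermekimab doses in every treated participant might seem the natural remedy. The documents do not say whether Arm 2's Week 2 injection is active or placebo. If it is placebo, that arm's third active dose falls at Week 3, which has no 30-minute observation.

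**Conclusion.** The mismatch is real and rests on stated rules, not on missing detail. The protocol requires 30-minute observation and AE assessment at Weeks 16, 17 and 18, and the SAP's dedicated summary stops at Week 2. Arm 3 therefore contributes only placebo injections to it.

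The size is modest. The table leaves out first bermekimab exposure in up to about 50 of 150 participants, or about 40 of 140 under the assumed 20% loss. With no events, the upper limit would be about 3.0% as planned, against 2.0% to 2.1% with the crossover participants added. These figures assume equal arms of 50, and the lower limits hold only if pooling the two kinds of first exposure is accepted.

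The primary efficacy analysis is unaffected, and reactions reported as AEs remain in the general tables. The missing item is the acute 30-minute incidence on first exposure in the crossover arm. It is worth correcting because the observation visits are already scheduled.

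**What to change.** Extend the SAP 6.1 summary from Weeks 0, 1 and 2 to include Weeks 16, 17 and 18, by treatment group, with a separate Placebo→bermekimab 400 mg qw column. The SAP already defines that group in section 6. Show Arm 3's single-injection first exposures separately from the two-injection loading doses of Arms 1 and 2, and do not report them only as a pooled figure.

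If the eCRF has no dedicated field at Weeks 16 to 18, derive the events from AE onset date and time relative to the injection, and name that source in a footnote. The treatment-emergence rule in SAP 6.1 refers to event time and administration time, which suggests that such times are collected. The downside is that the two halves of the table would then rest on different methods of capture, so a lower count at Weeks 16 to 18 could partly reflect less specific recording.

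If the sponsor prefers to keep the table to Weeks 0 to 2, SAP 6.1 should say so, give the reason, and point to where reactions at Weeks 16 to 18 are reported.

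The cost is a changed sentence and one extra table, plus the derivation if there is no dedicated field. No visit, assessment or treatment rule changes.
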